6.1 Discontinuing

Withdrawal criteria

Participants will be informed that they have the right to withdraw from the study at any time, without prejudice to any medical care (such that might be required if we incidentally identify a medical condition), and are not obliged to state their reasons. Additionally the investigator may withdraw a participant at any time for the following reasons:

- If any of the study exclusion criteria are diagnosed
- Protocol violations
- Adverse events

Discontinuation of the study

The study may be discontinued at any time on the advice of the responsible principal investigators on the basis of new information regarding safety. A Data Safety Monitoring Board has been constituted to provide advice to the investigator team with regard to participant safety (Section 15.1). Additionally, the study may be terminated if progress is unsatisfactory.

In the case of premature termination or suspension of the experiment, the investigator will inform the study participants and ensure appropriate follow up in the unlikely event this is required clinically. In addition, the appropriate ethics committee will be informed.

Procedure to withdraw

Participants with clinically significant abnormalities requiring discontinuation will be followed until recovery from the abnormality. If the study is discontinued for safety reasons, the investigators will contact all affected participants within a week to inform them of the termination of their involvement in the study. Participants discontinuing from the study may be replaced. A new participant number must be issued for the new participant.

If a participant fails to respond to telephone contact or is consistently unavailable for home visit, attempts will be made to ensure that the reason for not communicating is not an adverse event (bearing in mind that the participant is not obliged to state his/her reasons).

7. Outcomes

Primary outcome measure:

Changes in wake after sleep onset (WASO) as determined by 4 EEG channel polysomnography with portable recorder at baseline, 3 and 6 months. We will compare the differences between infrasound and sham sound.

Secondary outcome measures:

EEG parameters from the overnight sleep studies - Sleep latency, sleep staging, sleep stage shifts, arousal frequency and power spectral analysis for sleep microarchitecture analysis.

Tertiary Outcome Measures:

Neurocognitive tests (Section 12.8):

N-back

Tower of London

Cardiovascular and stress measures (Section 12.9):

Office blood pressure

Pulse wave velocity

Heart rate variability

Blood markers- highly sensitive CRP, interleukin (IL)-6, TNF-alpha and HbA1c

Hair Cortisol

Neurotological tests (Section 12.4):

Vestibular Evoked Myogenic Potentials (VEMP)
Video Hit Impulse Tests (vHIT)
Audiometry
Otoacoustic Emissions (OAE)
Videonystagmography (VNG)
Matted Romberg test
Unterberger test
Vestibular Event Monitoring

Screening, Phenotyping and Explanatory Questionnaires and measures (Appendix B & C):

Insomnia Severity Index (ISI) questionnaire
Weinstein's Noise Sensitivity Scale (WNS) score
Depression Anxiety and Stress Scale (DASS-21)
Kessler 10 (K10)
EYSENCK Personality Questionnaire-Revised
Noise Annoyance Scale
Symptom Visual Analogue Scales
Warwick Edinburgh Mental Well-being Scale
Ethnicity
Medical history
Medication
Sleep Disorders and Patterns
Epworth Sleepiness Scale
Health and Work Performance Questionnaire
Shift work questionnaire
Attitudes on Windfarms
Exit questionnaire

Table 1. Screening and Outcomes Measurements

[figure not shown]
Item	Staff	Screening	Baseline	3month	6month
Screening - online					
Weinstein's Noise Sensitivity Scale (WNS)		X			
Cardiovascular, sleep, or neurological chronic illness			X		
Clinically significant sleep disorders		X			
Major psychiatric disorder		X			
Hypnotic or anti-psychotic medication		X			
Shiftwork Questionnaire		X			
Breastfeeding, Pregnant or planning pregnancy		X			
Child under the age of 5 years		X			
Insomnia Severity Index		X	X	X	X
Epworth Sleepiness Scale			X	X	X
DASS-21			X	X	X
Kessler-10			X	X	X
Attitudes on Wind farms			X		
Exit Questionnaire					X
Screening – home					
Actigraphy and Consensus sleep diary (7 nights)		X			
Audiometry		X			
Clinical Assessments - home					
Sleep and Wake Measurements					
Home 4 EEG channel polysomnography (1 night)			X	X	X
Neurobehavioural and neurocognitive performance			X	X	X
Actigraphy (7 nights prior to PSG)			X	X	X
Sleep Disorders and Patterns Questionnaire			X	X	X
Cardiovascular and Stress measurements					
Height, Weight, Waist circumference			X	X	X
Office Blood Pressure			X	X	X
hsCRP			X	X	X
IL-6			X	X	X
TNF-alpha			X	X	X
Hair cortisol			X	X	X
HbA1c			X	X	X
Pulse wave velocity			X	X	X
Annoyance and Wind Turbine Syndrome measurements					
Visual Analogue Scale questionnaire			X	X	X
Noise Annoyance Scale			X	X	X
Psychological measurements					
EYSENCK Personality Questionnaire-Rev.			X		
Warwick Edinburgh Mental Well-being Scale			X	X	X

(WEMWBS)					

Item	Staff	Screening	Baseline	3month	6month
Clinical Assessments - home					
Neuro-otological measurements					
Audiometry (inc. tympanometry,otoscopy)			X	X	X
Vestibular Evoked Myogenic Potentials (VEMP)			X	X	X
Video Hit Impulse Tests (vHIT)			X	X	X
Audiometry			X	X	X
Otoacoustic Emissions (OAE)			X	X	X
Videonystagmography (VNG)			X	X	X
Matted Romberg test			X	X	X
Unterberger test			X	X	X
Vestibular Event Monitoring			X	X	X

8. Participant timeline

Figure 1: Timeline for study protocol

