5.2 Exclusion criteria

1. Rotating shift worker
2. Planning to be away from home for more than a month during the study period

3. Major psychiatric disorders
4. Use of any hypnotic medications or other medications that interfere with sleep within the last month
5. Breastfeeding, pregnant or attempting to become pregnant women in the household
6. Young children (under 5 years) living in the home

6. Study Interventions

Participants that meet the eligibility criteria will be randomised to either:

- 1) simulated wind turbine sound at 93dB Pk (infrasound, test exposure)
- 2) absence of sound (sham, control exposure).

Four 600mm x 600mm cube speakers (photo below) will be installed in the bedroom of each participant. For participant convenience, these speakers can be placed in variable configurations within the participant's bedroom. The speakers are wired together and are powered by a single cord that plugs into a domestic power point.

In addition to the speakers there will be two microphone stands with microphones placed in the bedroom. Neither microphone will collect sound content or conversation, but they will collect the sound level in decibels of 1) infrasound and 2) audible sound.

The speakers and microphones will operate continuously over the six month period of the study. By agreement with the participant, the acoustic engineer will schedule regular visits to the home to assess the correct functioning of the equipment. These visits may be up to weekly in the first month of operation and then monthly or as required for the remaining five months of operation. All participants will be reimbursed for expenses associated with the use of electricity to run the speakers. The acoustic engineer will be unblinded to group allocation and will be the contact point for participants who want to discuss anything regarding the speakers, microphones, electricity consumption or other exposure related query, thus ensuring the participant and clinical assessment staff remain blinded to group allocation.

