8.4 Reimbursement

Participants will be fully reimbursed for the additional cost of electricity for running the speakers and microphones. We anticipate that this amount will be in the range of \$60 to \$120. We will offer a payment of \$1,000 to cover electricity and the inconvenience of having the speakers in the home and participating in the testing for all participants involved in this study.

9. Sample size

From previous studies, the between-subject standard deviation in wake after sleep onset (WASO) is conservatively estimated at 20 minutes. Most trials of treatments for insomnia, for instance, regard a change of 15 minutes or more in WASO as being clinically meaningful. A sample size of 120 participants (which includes allowance for 22 dropouts) will have 85% power to detect a 0.25 effect size (Cohen's f).

10. Recruitment

Number and source of participants

The target number of participants is 120. This will provide 60 participants in the infrasonic group and 60 participants in the sham group.

Participants will be found by public advertising in local newspapers, community radio, television media and social media through the Woolcock website and its database of

research volunteers which will direct all volunteers to the online screening website (Appendix A).

11. Methods: Assignment of interventions

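### Section 6.1 allows withdrawal after randomisation on grounds that disturbed sleep can trigger and states no later PSG, so 6-month WASO can be lost selectively if infrasound does harm

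*Protocol*

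**What the plan says.** Section 6.1 gives the investigator discretion: "Additionally the investigator may withdraw a participant at any time for the following reasons". Three grounds follow: "If any of the study exclusion criteria are diagnosed", protocol violations, and adverse events.

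The exclusion criteria in section 5.2 include "Major psychiatric disorders" and "Use of any hypnotic medications or other medications that interfere with sleep within the last month".

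On what happens next, section 6.1 says: "Participants discontinuing from the study may be replaced. A new participant number must be issued for the new participant". The only follow-up it describes is clinical: "Participants with clinically significant abnormalities requiring discontinuation will be followed until recovery from the abnormality". Nothing in the protocol says that a withdrawn participant is still asked for the 3- or 6-month PSG.

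Section 7 makes change in PSG-measured WASO the primary outcome. Section 14 takes the 6-month difference as the primary endpoint, from a mixed model with baseline, 3-month and 6-month values. Section 9 sets 120 participants, "which includes allowance for 22 dropouts".

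**The concern.** Two of the three withdrawal grounds can be set off by the effect under study. A participant whose sleep deteriorates may start a sleep aid or receive a psychiatric diagnosis, both of which touch section 5.2. The same participant may report sleep disturbance, dizziness, palpitations or panic as adverse events, and section 1 lists these among the symptoms attributed to wind turbines.

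Such a participant could be identified before the endpoint. Table 1 repeats the Sleep Disorders and Patterns questionnaire, DASS-21 and K10 at 3 months, and that questionnaire (Appendix C) asks about medication for diagnosed insomnia.

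If withdrawal then ends follow-up, the missing 6-month values belong disproportionately to the worst sleepers, and more of them come from the infrasound arm if infrasound is harmful. The trial is meant to settle a disputed question of harm, so a null result would be open to the reply that affected people had been taken out. An analysis plan cannot repair this, because the recording would not exist.

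**Working it through.** **Inputs from the protocol.** SD of WASO 20 min, effect size f = 0.25, 15 min described as clinically meaningful, 120 randomised with 22 dropouts allowed, 60 per arm (sections 9 and 10).

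**Assumptions, not in the protocol.** Normal WASO, correlation 0.5 between visits, two-sided alpha 0.05, and the withdrawal rates below.

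**The plan's own figure.** For two groups f = 0.25 means d = 2 × 0.25 = 0.5, or 0.5 × 20 = 10 min. Evaluable N = 120 − 22 = 98. A between-group repeated-measures test with three measures has λ = f²·N·m / [1 + (m − 1)ρ] = 0.0625 × 98 × 3 / 2 = 9.19 on (1, 96) df. Power is 85.1%, against the stated 85%. This only places 10 min as the effect planned for; the bias calculation does not depend on it.

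**Withdrawal model.** Take as threshold the value that 10% of the sham arm exceed: c = 20 × 1.2816 = 25.6 min above the sham mean. Withdraw a fraction q of everyone above c. For an arm with mean μ, let a = (c − μ)/20 and p = 1 − Φ(a). The mean of those who remain is

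μ − 20·q·φ(a) / (1 − q·p).

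Example, true difference 10 min and q = 0.5:
- Sham: a = 1.282, φ = 0.1755, p = 0.100. Mean = 0 − 1.755/0.950 = −1.85.
- Infrasound: a = 0.782, φ = 0.2939, p = 0.217. Mean = 10 − 2.939/0.891 = 6.70.
- Difference among completers: 6.70 + 1.85 = 8.55 min.

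**Mixed model.** A large-sample simulation used the same threshold, with a normal model using all observed visits. In the late case, withdrawal falls between months 3 and 6 and is driven by the 6-month value, which is lost. In the early case, it is driven by the 3-month value, and both follow-up values are lost.

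| True (min) | q | Withdrawn, infrasound vs sham | Completers, late | Mixed model, late | Mixed model, early |
|---|---|---|---|---|---|
| 10 | 25% | 5.4% vs 2.5% | 9.4 | 9.6 | 9.9 |
| 10 | 50% | 10.9% vs 5.0% | 8.6 | 9.0 | 9.6 |
| 10 | 100% | 21.7% vs 10.0% | 6.4 | 7.3 | 9.1 |
| 15 | 25% | 7.4% vs 2.5% | 14.0 | 14.3 | 14.8 |
| 15 | 50% | 14.9% vs 5.0% | 12.8 | 13.5 | 14.4 |
| 15 | 100% | 29.8% vs 10.0% | 9.0 | 10.4 | 13.4 |

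With a true difference of 0 the estimate stays at 0 in every scenario, apart from simulation noise of at most 0.1 min.

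**Plausibility of the rates.** At a true 10 min and 60 per arm, q = 50% means 60 × 0.109 + 60 × 0.050 = 9.5 withdrawals. q = 100% means 60 × 0.217 + 60 × 0.100 = 19.0, or 86% of the 22-dropout allowance, all driven by WASO. That row is an extreme.

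**The case against.** The rule is permissive: the investigator may withdraw and participants may be replaced. Bias needs three things together: a real harmful effect, a withdrawal ground that follows from poor sleep, and a decision to use the discretion. This stands, and it makes the finding conditional.

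The hypnotic route is the less clear one. The trigger speaks of criteria being diagnosed, which suits psychiatric disorder better than medication use. Criterion 4 is framed for entry, and Table 1 lists hypnotic medication at screening only. Use first noticed at the 6-month visit need not cost that visit's PSG. But the rule covers any exclusion criterion, use could come to light at month 3 or between visits, and the adverse-event ground does not depend on this reading.

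The planned mixed model uses earlier visits and recovers part of the loss. That also stands, and its figures should be preferred to raw completer means. It cannot recover the part that depends on values never observed.

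How collected data are analysed, and how sleep medication is handled, may properly sit in the SAP. Whether the PSG is collected at all is a protocol matter.

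A reader might also infer three stronger points that the protocol does not support:
- That better sleepers fill the vacated places. Nothing says how replacements are allocated or that they differ from other eligible people. The bias comes from the missing outcomes.
- That replacement double-counts the 22 dropouts. Doing both only adds evaluable participants.
- That exclusion criteria should cease to apply at randomisation. That would alter the grounds for stopping exposure, which the statistical problem does not require.

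**Conclusion.** The weakness is real but conditional. Section 6.1 allows outcome-related withdrawal from the study after randomisation and states no PSG afterwards. If infrasound worsens sleep and the discretion is used on affected participants, the 6-month effect is biased toward zero. Under no effect this mechanism produces no bias, so it cannot create a false finding of harm.

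For a true 10 min, partial use of the discretion (25 to 50% above the threshold) costs about 0.4 to 1.0 min in the late mixed-model case and less in the early case. The extreme case costs about 2.7 min. These figures rest on SD 20, normality, correlation 0.5 and assumed withdrawal rates. They show direction and rough scale and do not forecast the loss. A reader might infer that the rule will remove everyone whose sleep is disturbed, so that a true 10 min would appear as about 7. The permissive wording does not support that as the expected result.

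**What to change.** Leave the grounds for stopping exposure as they are. In section 6.1, separate stopping exposure from leaving outcome follow-up, and add:

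- Every randomised participant who still consents is asked for the 3- and 6-month PSG and questionnaires, whether or not exposure has stopped.
- Any sleep medication started is recorded with dates, and the plan states how it is handled. A hypnotic may itself change WASO, so continued follow-up alone does not settle what is being estimated.
- All randomised participants are analysed in the arm to which they were randomised.
- A replacement may add a participant but does not remove the person replaced from follow-up or analysis.

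The cost is protocol wording and keeping a few home visits that the schedule already contains. The change has to precede the withdrawals it covers, because a missed PSG cannot be recovered.

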8.3 Infrasonic or Sham speaker installation and monitoring

The acoustic engineer will schedule a visit to the home soon after baseline testing has been completed. At this visit, either infrasonic or sham speakers will be installed into the bedroom of the participant. In addition to the 4 x 600mm cube speakers we will place a monitoring box and 2 microphones in the bedroom.

The acoustic engineer is unblinded and will advise participants that if they have any concerns about the speakers that they should contact him directly and not discuss this with other members of the team who do not know what type of speaker is installed in the bedroom. Additionally, the participants will be informed that their electricity bill may increase and that they will be reimbursed for this expense. Again, this is to be discussed with the unblinded acoustic engineer who installed the speakers and not any other member of the team.

The acoustic engineer will arrange regular visits to the home of participants to check that they speakers are performing as designed and that the monitoring equipment is collecting infrasonic or sham sound exposure information. These visits will be weekly in the first month, then monthly for the next five months or as required. He will download data and bring this back to Woolcock Institute for secure storage.

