11.2. Blinding

Expectations on the part of participants and investigators may influence the effect of the exposure (infrasound) and, more particularly, may influence the measurement of those effects, especially the subjective (self-reported) outcomes. To avoid the potential for this measurement bias, it is important that both participants and the investigators who are measuring outcomes are blinded to the intervention group. Fortunately, as infrasound is, by definition, inaudible, this is readily achieved by the use of a sham device that appears the same as the infrasound device, but which does not produce any sound. Only the unblinded acoustic engineer will have knowledge of the exposure and they will never disclose this group allocation to the participants or staff/investigators who interact with participants.

12. Methods: Description of study procedures

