15.1 Data monitoring

Because infrasound like this has not been used in experiments of longer than 2 hours duration a Data Safety Monitoring Board has been convened. The DSMB will oversee participant safety in both the laboratory study (Protocol No X16-0073 & HREC/16/RPAH/91) and this community based study by reviewing unblinded accumulated safety data pertaining to infrasound.

16. Adverse Events Reporting

Collection of adverse events will occur throughout the study.

Serious adverse events (SAE) are defined as any untoward medical occurrence that:

- Results in death
- Is an immediately life-threatening condition
- Requires hospitalisation or prolongs hospitalisation
- Results in persistent or significant disability/incapacity
- Is a congenital anomaly/birth defect
- Results in any other important medical condition.

The Ethics Committee will be notified of any SAE within 72 hours.

17. Auditing

The study will not be externally audited

18. Ethics and dissemination

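### Section 6.1 allows a week to tell participants of a safety stop, while inaudible bedroom speakers could run for up to seven more nights

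*Protocol*

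**What the plan says.** Section 6.1 of the protocol deals with stopping in two places. Under the heading on discontinuation of the study it says "In the case of premature termination or suspension of the experiment, the investigator will inform the study participants", with no interval. Under the procedure to withdraw it says "If the study is discontinued for safety reasons, the investigators will contact all affected participants within a week". This is the only interval given for telling participants. The same subsection foresees people who are hard to reach: "If a participant fails to respond to telephone contact or is consistently unavailable for home visit".

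Four other places bear on how that week works in practice:

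- Section 6, on operation: "The speakers and microphones will operate continuously over the six month period of the study". On power supply: "The speakers are wired together and are powered by a single cord that plugs into a domestic power point".
- Section 8.3, on the engineer's visits: "These visits will be weekly in the first month, then monthly for the next five months or as required". Section 6 is looser and says visits in the first month may be up to weekly.
- Section 11.2, on why blinding is easy to achieve: "as infrasound is, by definition, inaudible".
- Section 15.1, on why a Data Safety Monitoring Board (DSMB) was set up: "infrasound like this has not been used in experiments of longer than 2 hours duration".

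No section describes a remote shut-off, an instruction to unplug, or any other step that ends the exposure when a safety stop is called.

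**The concern.** In many trials a week to notify participants does no harm, because exposure ends at the clinic visit or the participant controls the dosing. Here the exposure is delivered every night by equipment in the bedroom until someone acts. The participant cannot hear it and does not know which arm they are in. Without a call they have no reason to pull the plug.

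The team would stop for safety because of new information about an exposure whose longer-term effects are, on the protocol's own account, untested in experiments beyond two hours. The DSMB's advice protects participants only as fast as it reaches the home. The written limit would let a reachable person sleep in the exposure for a further week in full compliance with the protocol. This concerns participant safety; it does not touch the randomisation, endpoint, power or analysis.

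**Working it through.** No sample-size or error-rate formula is involved. The check is a reading of the sections together, with simple arithmetic on the size.

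**Inputs**
- Notice limit: 7 days (Section 6.1).
- Operation: continuous for six months, taken as 365/2 = 182.5 nights (Section 6).
- Active arm: 60 participants planned, of 120 in total (Section 10).
- Engineer visits: weekly in month 1, then monthly for five months (Section 8.3); up to weekly in month 1 (Section 6).
- Serious adverse event notice to the ethics committee: 72 hours (Section 16).

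**Longest exposure before notice is due**
- 7 nights, or 7 × 24 = 168 hours of speaker operation.
- Share of planned nights: 7 / 182.5 = 3.8%.
- Under a 24-hour rule (assumed), the maximum falls to about 1 night, or 24 hours.
- For scale only: 168 − 72 = 96 hours, so the limit is four days longer than the one Section 16 sets for reporting a single serious adverse event. The two rules have different purposes and do not contradict each other.

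**Would a scheduled engineer visit end the exposure sooner?** Assume visits are evenly spaced and homes are spread evenly over the six months.
- Months 2 to 6, monthly visits: 7 / 30.4 = 23% of homes have a visit in a given week.
- Month 1, weekly visits: 100%.
- Overall: (1 × 1.00 + 5 × 0.23) / 6 = 2.15 / 6 = 36%, leaving 64% without a visit.
- If visits are monthly throughout: 23% with, 77% without.

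So roughly 64% to 77% of homes would have no scheduled visit in the week. As-required visits would lower this. These shares show only that the routine schedule does not close the gap. They do not estimate how many people would be told late, since notice would normally go by telephone.

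**Cost of prompt calls:** 120 × 5 to 10 minutes (assumed) = 600 to 1,200 minutes = 10 to 20 hours.

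**The case against.** The strongest reply is that the sentence governs notification, not exposure. It sets an outer limit for telling people that their involvement has ended, and it does not say the speakers stay on until then. Continuous operation is tied to the study period, and a stopped study is arguably outside it. The separate duty to inform on termination or suspension carries no week's grace. The means for quick action already exist: as-required visits, an unblinded engineer as equipment contact, a single plug, and a DSMB that can press for urgency. An individual with an adverse event can be withdrawn at any time. Participants agreed to about six months of exposure, Section 1 says there is as yet no evidence that the proposed physiological effects occur, and no document given here makes 24 or 72 hours the right figure.

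Much of this stands. The seven nights are a worst case that needs a team to use its full allowance. No harm is shown, the whole active arm would be exposed only if all of its homes were running at once, and the replacement interval is a matter of judgement. But the separate duty to inform has no deadline, so it does not shorten the week. The visits, the plug and the DSMB show that faster action is feasible; nothing in the text requires it. A participant's freedom to withdraw or unplug does not help someone who has not heard of the stop. The week is useful for people who cannot be reached, but that does not justify applying it to those who can.

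**Conclusion.** The concern holds. The protocol states a notice limit that suits a continuous, inaudible bedroom exposure badly, and no other section shortens it or switches the speakers off first. The upper bound is seven further nights per active-arm participant, about 3.8% of planned nights, in at most 60 participants. It rests on a safety stop occurring, on contact being left to the end of the permitted week, and on the speakers running until contact. The probability of a stop is not given and is not estimated here. The change should be made because it is cheap and protects participants; the trial's inference does not depend on it.

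**What to change.** Amend Section 6.1 so that, on a safety stop or suspension:

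1. All participants in both arms are telephoned promptly, within a short interval agreed with the DSMB (for example 24 hours, and no more than 72).
2. Each receives the same scripted instruction to unplug the speakers. The unblinded engineer, already the contact for equipment, can make the calls. Giving the same call to both arms keeps allocation concealed.
3. Anyone not reached by telephone gets an as-required visit.
4. One week remains as the backstop for formal notification and follow-up.

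The cost is a wording amendment and a current contact list. If a stop occurs, add at most 120 calls, about 10 to 20 hours in all at the assumed call length, and a few visits to homes not reached. No extra participants or scheduled visits are needed.
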